5.5.4 ANTICIPATED RECRUITMENT, ENROLLMENT, AND RETENTION

We anticipate needing to recruit a total of 175 participants to achieve our target enrolment of 70 eligible participants after the phone and in person screening session (See Figure 5). With all these measures, we expect greater than an 80% retention rate or better for the end of treatment follow-up (See Figure 5).

Figure 5. Consort Diagram

6 STUDY INTERVENTION(S) OR EXPERIMENTAL MANIPULATION(S)

6.1 STUDY INTERVENTION(S) OR EXPERIMENTAL MANIPULATION(S) ADMINISTRATION

6.1.1 STUDY INTERVENTION OR EXPERIMENTAL MANIPULATION DESCRIPTION

6.1.1.1 COGNITIVE BEHAVIORAL THERAPY

BACKGROUND AND RATIONALE FOR CBT-I

CBT for insomnia is based largely on Spielman's conceptual model for primary insomnia. This model identifies predisposing factors, precipitating events, and perpetuating mechanisms that contribute to the development of chronic insomnia. Some individuals may be particularly predisposed or vulnerable to sleep difficulties by virtue of having a highly sensitive, or malfunctioning biological sleep system or a hyperactive arousal system that interferes with sleep. Circumstances such as stressful life events often precipitate sleep difficulties. This is more likely to occur in individuals with a predisposition for insomnia. In most cases the sleep difficulties are transient and resolve when the original distress subsides. In some cases, the patient becomes overly focused on the sleep problem. This focus tends to perpetuate sleep difficulties as it can produce heightened anxiety about sleep and lead to the development of maladaptive strategies and practices that, although intended to improve sleep, actually worsen it. Such maladaptive strategies include avoidance behaviors during waking hours (e.g., cancelling planned activities due to fatigue or fear such activities will interfere with next night's sleep), varying bed time and/or wake time, spending excessive time in bed, and developing rigid sleep-related rituals.

These behaviors are manifestations of increased sleep effort. Simply stated, the patient is trying too hard to sleep. In response to poor sleep patients also develop sleep-interfering cognitions, such as overestimating and worrying about the negative consequences of poor sleep, approaching bedtime with fear of failure, etc. Thus, patients' cognitive responses to their sleep problems and many of the practices that they adopt for coping with it end up prolonging or exacerbating the very problem they are trying to solve. The cognitive-behavioral approach to insomnia aims to modify behaviors that sustain or add to patients' sleep problems and correct cognitions that lead to heightened anxiety about sleep and to maladaptive sleep-related behaviors.

6.1.2 ADMINISTRATION AND/OR DOSING

CBT-I will consist of 6 sessions administered ideally once a week over a period of six to eight weeks. A full-dose will be defined as completing all 6 sessions. Sessions will occur either face-to-face or via Stanford Zoom with a PhD/PsyD psychologist, or graduate student under the supervision of a licensed PhD/PsyD psychologist, who is experienced in administering the study treatments and has completed the CBT-I training. Study sessions will occur in treatment rooms at Stanford or via Stanford Zoom. The full description of treatment details can be found in Section 6.1.1, Study Intervention or Experimental Manipulation Description and Appendix C.

6.2 FIDELITY

6.2.1 INTERVENTIONIST TRAINING AND TRACKING

All treatment sessions will be audio and/or video recorded, and the recordings will be securely uploaded to an encrypted server. Treatment fidelity will be monitored in a randomly selected subset of 10% of the sessions. Treatment fidelity will be rated using a treater fidelity questionnaire (Appendix D).

6.3 MEASURES TO MINIMIZE BIAS: RANDOMIZATION AND BLINDING

6.3.1 RANDOMIZATION PROCEDURES

N/A

6.3.2 BLINDING PROCEDURES

N/A

6.4 STUDY INTERVENTION/EXPERIMENTAL MANIPULATION ADHERENCE

Since compliance with CBT treatment elements has been found to be variable, it will be measured for potential influence on outcomes¹¹². Weekly review of daily sleep logs and their correspondence with actiwatch data will be used as an additional proxy of treatment compliance during the course of treatment. At the end of treatment participants will complete a treatment adherence questionnaire explicitly designed for CBT-I¹¹⁴. We have used this method to check for compliance in earlier research¹¹⁵.

6.5 CONCOMITANT THERAPY

For this protocol, participants may not use psychotropic medications that may significantly impact sleep, alertness, or mood until after visit 9 (end of treatment). The use of medications specifically used for sleep are not allowed during until after visit 9 (end of treatment). Medication usage will be assessed at each study visit and documented in the relevant Case Report Form (CRF).

Participants may not receive cognitive behavioral therapy for other conditions (e.g. depression) until after visit 9 (end of treatment).

6.5.1 RESCUE THERAPY

N/A

7 STUDY INTERVENTION/EXPERIMENTAL MANIPULATION DISCONTINUATION AND PARTICIPANT DISCONTINUATION/WITHDRAWAL

7.1 DISCONTINUATION OF STUDY INTERVENTION/EXPERIMENTAL MANIPULATION

When a participant discontinues from CBT-I but not from the study, remaining study procedures will be completed as indicated by the study protocol. If a clinically significant finding is identified (including, but not limited to changes from baseline) after enrollment, the investigator or qualified designee will determine if any change in participant management is needed. Any new clinically relevant finding will be reported as an adverse event (AE).

The data to be collected at the time of study intervention discontinuation will include the following:

 The reason(s) for discontinuing the participant from the intervention, and methods for determining the need to discontinue The participant will complete the emotional distress and sleep questionnaires that are administered at
each treatment session at the time of discontinuation. Thereafter, the participant will be included in all
future scheduled assessments (including emotional distress and sleep questionnaires), even though not
participating in the intervention.

7.2 PARTICIPANT DISCONTINUATION/WITHDRAWAL FROM THE STUDY

Participants are free to withdraw from participation in the study at any time upon request. An investigator may discontinue a participant from the study for the following reasons:

- Significant study intervention non-compliance, including repeated failure to complete sleep diaries, adhere to treatment protocol requirements (ex. prescribed sleep schedule), or engage productively in treatment sessions.
- Lost-to-follow up; unable to contact participant (see Section 7.3, Lost to Follow-Up)
- Any event or medical condition or situation occurs such that continued collection of follow-up study data would not be in the best interest of the participant
- The participant meets an exclusion criterion (either newly developed or not previously recognized) that precludes further study participation
- Increase in bothersome nightmares for a week under treatment. We have not seen consistent reporting of nightmares with the proposed treatments, however that is always possible, hence again we would want to make sure that that occurred for at least a week before a patient was discontinued.

Patients will be allowed to continue in the protocol after an SAE independent of treatment, e.g. hospitalization following a fall. All treatments are considered active and patients will be allowed to continue their treatment as a courtesy. Similarly, patients will be allowed to continue if it is discovered following treatment initiation that they meet an exclusion criterion (either newly developed or not previously recognized) if the study physician and psychologist deem there are no additional risks to the participant in continuing treatment. However, data from such participants will not be included in statistical analyses since such SAEs and other exclusions may affect sleep. Patients will not be restarted if their sleep deteriorates meeting the above criteria and they are discontinued from the protocol.

The reason for participant discontinuation or withdrawal from the study will be recorded on the electronic Case Report Form (eCRF). Participants who sign the informed consent form, but have not yet received the study intervention, and subsequently withdraw, or are discontinued from the study will be replaced.

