A Novel Use of a Sleep Intervention to Target the Emotion Regulation Brain Network to Treat Depression and Anxiety

NCT Number: 04424407

Stanford University IRB Protocol Number: 56961

Principal Investigator:

[name]

Department of Psychiatry and Behavioral Sciences

Stanford University School of Medicine

Sponsor/Funding Source:

National Institutes of Mental Health (NIMH)

Grant Number: R61MH120245

Statistical Analysis Plan

Document Date: May 25, 2025

Statistical Analysis Plan

Our general approach is to conduct a modified intent-to-treat analysis, in which all available data is included in analyses unless data are artifactual or corrupted. The primary hypothesis in this single-arm phase is that insomnia treatment using CBT-I will be associated with improvements in fronto-limbic brain emotional brain function. Specifically, we predict that sleep restoration will be associated with reduced amygdala reactivity and increased amygdalamPFC connectivity during emotion fMRI tasks. More specifically, we hypothesize that the reduction in amygdala emotional reactivity will be due to increased top-down regulatory control by interconnected cortical regions. Therefore, the primary analysis plan will be to first examine treatment-associated changes in amygdala reactivity across the three tasks, with FDR correction applied for each task. For tasks and contrasts in which amygdala reactivity is significantly reduced following treatment, we then test whether the reduction in amygdala reactivity corresponds to a parallel increase in connectivity with regions of the mPFC. We aim to test these hypotheses by applying linear mixed-effects (LME) models (R package "lme4"). Random intercepts at the individual participant level will be included in our models to account for the clustering of observations within individuals across time. All statistical models include age and sex as covariates of non-interest.

We also expect to replicate the previously reported improvements in depression and insomnia symptoms following CBT-I. Treatment-related changes in clinical outcomes (depression and sleep) will be tested using LME models with random intercepts. Given the zero-inflation in the measures of suicidal thinking (CSSRS and BSSI), we employ generalized LME models for the negative binomial family to examine treatment-related changes in suicidal thinking.

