4.3 JUSTIFICATION FOR INTERVENTION

The CBT-I intervention will be delivered according to protocols and materials from our large-scale VA implementation of CBT-I¹⁰⁸. The intervention materials include a published sleep self-help book, a published therapist guide, and the CBT-I therapist manual^{108,109}.

Participants must complete 5 sessions of treatment to have evaluable data for analyses related to the primary objectives to ensure there is sufficient improvement in sleep.

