9.3 POPULATIONS FOR ANALYSES

We will conduct both an intent-to-treat (ITT) analysis using the last observation carried forward and analysis based on completers only, to assess bias caused by dropouts. Emotional distress assessments during the weekly treatment sessions will aid in understanding reasons for dropout.

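### Section 7.2 allows withdrawal from the whole study for poor CBT-I adherence, so missing Visit 9 data can depend on adherence and the SAP's pre-post change can be overstated

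*Combined protocol and SAP*

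**What the plan says.** Protocol section 7.2 opens its list of grounds with "An investigator may discontinue a participant from the study for the following reasons". The first ground is "Significant study intervention non-compliance, including repeated failure to complete sleep diaries, adhere to treatment protocol requirements (ex. prescribed sleep schedule", and it goes on to cover unproductive engagement in sessions. The power is permissive, and it applies to the study as a whole.

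Section 7.1 deals with stopping treatment only: "When a participant discontinues from CBT-I but not from the study, remaining study procedures will be completed as indicated by the study protocol". Such participants stay in later scheduled assessments. The retention plan in 5.5.2 commits staff to keep trying to bring participants who do not comply back for later follow-ups.

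Section 6.4 treats adherence as something to study: "Since compliance with CBT treatment elements has been found to be variable, it will be measured for potential influence on outcomes".

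Three passages bear on who is analysed:

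- Section 4.3: "Participants must complete 5 sessions of treatment to have evaluable data for analyses related to the primary objectives".
- Section 9.3 plans an "intent-to-treat (ITT) analysis using the last observation carried forward and analysis based on completers only, to assess bias caused by dropouts".
- The 2025 SAP plans a "modified intent-to-treat analysis, in which all available data is included in analyses unless data are artifactual or corrupted". It uses mixed models with a random intercept, age and sex. It states no adherence term, no last observation carried forward (LOCF), no completers comparison and no sensitivity analysis for missing data.

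**The concern.** Two participants with equally little exposure to the active parts of CBT-I can be handled differently. One who stops treatment is still invited to Visit 9. One who stays but keeps neither the diary nor the sleep schedule may be withdrawn, and the Visit 9 fMRI, polysomnography and questionnaires are then not collected.

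The ground for removal is low exposure. The protocol itself expects low exposure to give less benefit: section 4.3 justifies its session minimum by the need for enough improvement in sleep. Missing post-treatment data would then be related to the outcome. There is no control arm in which similar losses could offset this, and a rule to use all available data cannot supply a scan that was not taken. Removing poor adherers also narrows the adherence range that section 6.4 wants to relate to outcome.

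**Working it through.** **The plan's own figure.** Section 9.2 enrols 70 and plans to retain at least 80%: 70 × 0.80 = 56, which reproduces. Up to 14 of 70 may be lost.

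**Inputs the documents do not give (assumptions).**

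- w, the share withdrawn for non-compliance: taken as 5% to 20%. The upper end assigns the entire loss allowance to this one ground, so it is a ceiling.
- f, the effect in those withdrawn relative to adherers: taken as 0 to 1.

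**Formula.** Let A be the mean change in adherers. With everyone scanned, the mean change is A × [(1−w) + w·f]. With the withdrawn participants unscanned, the available post-treatment data estimate A. The ratio is 1 / [(1−w) + w·f].

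| w | f = 0 | f = 0.5 | f = 1 |
|---|---|---|---|
| 5% | 1/0.95 = 1.05 | 1/0.975 = 1.03 | 1.00 |
| 10% | 1/0.90 = 1.11 | 1/0.95 = 1.05 | 1.00 |
| 15% | 1/0.85 = 1.18 | 1/0.925 = 1.08 | 1.00 |
| 20% | 1/0.80 = 1.25 | 1/0.90 = 1.11 | 1.00 |

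**Does the SAP's model avoid this?** A random-intercept model was simulated with 70 participants, intraclass correlation 0.4, a change of −0.50 SD in adherers and 20% unscanned at follow-up (all assumed; 300 replicates, age and sex omitted).

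- f = 0: estimate −0.50, against −0.40 with full follow-up.
- f = 0.5: −0.50 against −0.45.
- f = 1: −0.51 against −0.51.

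A participant with only a baseline scan adds almost nothing to the estimated change.

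**LOCF under section 9.3.** For a measure taken only at baseline and Visit 9, carrying the baseline forward sets the change to zero. The ratio to full follow-up is (1−w) / [(1−w) + w·f]. At w = 20% it is 1.00 for f = 0, 0.80/0.90 = 0.89 for f = 0.5 and 0.80 for f = 1. For f of 0 or more, LOCF is never inflated and is often too small. For f between 0 and 1, the LOCF and available-data estimates therefore bracket the full-follow-up value.

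**The Go rule.** The amygdala criterion in 3.1.1 is M − SD/2 ≤ −0.35, not M ≤ −0.35. Suppose the mean moves from −0.28 with everyone scanned to −0.28/0.80 = −0.35 after 20% removal with f = 0. At M = −0.28 the criterion is already met once SD ≥ 2 × (0.35 − 0.28) = 0.14. With SD 1 in each subgroup, the whole-cohort SD is √(1 + 0.8 × 0.2 × 0.35²) = 1.01. The boundary is then −0.28 − 0.505 = −0.79 with everyone and −0.35 − 0.50 = −0.85 after removal. Both pass.

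**The case against.** The strongest reply has five parts.

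- **No literal conflict.** Section 7.1 is limited to people who remain in the study, and 7.2 covers leaving it. This stands. A reader might infer that 7.2 breaks 7.1, but the two differ in intent, not in wording.
- **Discretion.** The power is optional and aimed at significant or repeated failure. Section 5.5.2 points staff the other way, and every removal counts against the 80% retention milestone. This stands as a reason to expect sparing use. A reader might infer that scans are in fact lost and the effect is in fact overstated; the documents support only that this can happen.
- **LOCF.** Section 9.3 plans LOCF beside a completers analysis to expose dropout bias, and under a zero-change assumption LOCF returns the full-cohort mean. This stands for the protocol. The SAP mentions neither analysis.
- **The session minimum in 4.3.** Primary-objective data already require five sessions, so 7.2 mainly adds people who attend but do not adhere. This limits the size. But an analysis exclusion can be reversed because the data exist; a visit that was not held cannot.
- **Remaining data.** Ordinary partial adherence stays in the sample, and BDI and the suicidality scales are collected weekly. A reader might infer that the results would describe adherent participants only; that goes too far. The measures with no weekly reading, fMRI and polysomnography, are the most exposed.

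**Conclusion.** The concern holds as a conditional one. Section 7.2 permits adherence-dependent loss of Visit 9 data. If the power is used and those removed would have improved less, the SAP's mixed model and the protocol's completers analysis overstate the pre-post change. The overstatement is at most 25% in the range considered (w = 20%, f = 0), 11% at w = 20% with f = 0.5, and nil at f = 1. The direction rests on the protocol's own expectation that exposure matters. The size rests on assumed w and f.

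A reader might infer that a mean moved from −0.28 to −0.35 tips the Go decision. It does not follow, because the rule uses M − SD/2 and both cases pass under the SDs examined. The point is worth correcting because the remedy is cheap. It does not by itself undermine the trial's conclusions.

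**What to change.** Reconcile protocol sections 4.3, 5.5.2, 7.1, 7.2 and 9.3 with the SAP on who is followed and who is analysed. State that intervention non-compliance alone does not end scheduled assessments, and that these participants are invited to Visit 9 unless they withdraw consent or another 7.2 ground applies. Leave the other 7.2 grounds and all decisions about treatment as they are.

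The SAP already reports residual diagnostics on change scores, so follow-up may be complete. In that case:

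- report from the eCRF, where 7.2 has discontinuation reasons recorded, how many were withdrawn on this ground;
- add a sensitivity analysis for their missing post-treatment data, for example assuming no change, alongside the ITT and completers comparison of section 9.3;
- correct the text before it is reused in the R33 phase.

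The cost is a short clarification and one extra analysis; Visit 9 is already in the schedule for every participant. The downside is that some of those invited will not attend, and the estimated change may be less favourable.

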7.3 LOST TO FOLLOW-UP

A participant will be considered lost to follow-up if he or she receives treatment and fails to return for 3 scheduled visits and study staff are unable to contact the participant after at least 3 attempts.

The following actions must be taken if a participant fails to return to the laboratory for a required study visit:

Study personnel will attempt to contact the participant, the ideal will be to reschedule the missed visit
within one week for treatment sessions, and within two weeks for the end of treatment visit, counsel

the participant on the importance of maintaining the assigned visit schedule and ascertain if the participant wishes to and/or should continue in the study.

- Before a participant is deemed lost to follow-up, the investigator or designee will make every effort to regain contact with the participant (where possible, 3 telephone calls or emails and, if necessary, a certified letter to the participant's last known mailing address or local equivalent methods). These contact attempts will be documented in the participant's medical record or study file.
- Should the participant continue to be unreachable, he or she will be considered to have withdrawn from the study with a primary reason of lost to follow-up

8 STUDY ASSESSMENTS AND PROCEDURES

8.1 ENDPOINT AND OTHER NON-SAFETY ASSESSMENTS

8.1.1 PHYSICAL EXAMINATION

N/A

8.1.2 CLINICAL INTERVIEWS

DUKE¹¹⁶. The Duke Structured Interview for Sleep Disorders is a structured interview which screens for sleep disorders in accordance with criteria of both the DSM-IV and the international classification of sleep disorders (ICSD-2). The DUKE is composed of 4 modules that assess sleep disorder symptoms associated with complaints of insomnia, sleep disorders associated with complaints of hypersomnia, circadian rhythm sleep disorders, and sleep disorders associated with parasomnias.

MINI¹¹⁷.The Mini International Neuropsychiatric Interview is a brief structured diagnostic interview for DSM-IV and ICD-10 psychiatric disorders. It assesses the 17 most common mental health disorders selected based on current prevalence rates. The MINI uses branching tree logic.

8.1.3 QUESTIONNAIRES

Columbia Suicide Severity Rating Scale¹¹⁷ **. T**he Columbia Suicide Severity Rating Scale (CSSRS) is an assessment tool the evaluates suicidal ideation and behavior.

Beck Scale for Suicidal Ideation. The Beck Scale for Suicidal Ideation is a 21 questions evaluation of suicidal thinking that helps identify individuals at risk. It also helps measure a broad spectrum of attitudes and behaviors.

Insomnia Severity Index (ISI)¹¹⁸. The Insomnia Severity Index (ISI) is a 7-item self-report measure of insomnia type, severity, and impact on functioning. The items consist of: severity of sleep onset, sleep maintenance, early morning awakenings, sleep dissatisfaction, interference with daytime functioning, noticeability of sleep problems by others, and distress caused by sleep difficulties. Items are scored from 0 to 4 (0 = no problem, 4 = very severe problem). Score ranges of insomnia are: 0-7 absent, 8-14 subthreshold, 15-21 moderate, and 22-28 severe. The ISI has good validity and reliability.

Pittsburg Sleep Quality Index¹¹⁹. The Pittsburg Sleep Quality Index (PSQI) is a 19-item self-report questionnaire that measures sleep quality from seven categories: subjective sleep quality, sleep latency,

sleep duration, habitual sleep efficiency, sleep disturbances, use of sleeping medication, and daytime dysfunction. Items are scored from 0 - 3, and a global sum of 5 or greater indicates poor sleep quality. The PSQI has high validity and reliability (Cronbach's alpha = 0.83).

Dysfunctional Beliefs About Sleep (DBAS)¹²⁰. The DBAS-16 is self-report questionnaire consisting of 16 questions. The DBAS-16 uses a personal rating response format of 0-10 to assess 4 factors consisting of perceived consequences of insomnia, worry/helplessness about insomnia, sleep expectations, and medication.

Morningness Eveningness Questionnaire¹²¹. The MEQ consists of 19 questions that assess degree of alertness and activity associated with differences in morningness and eveningness. The MEQ mainly uses questions with a 4-choice format that correspond to a definite morning type, moderate evening type, and definite evening type.

Beck Depression Inventory (BDI)⁸⁹ . The BDI-II is a 21-item self-report scale that assesses the severity of depression symptoms. The depression items consist of: sadness, pessimism, past failure, loss of pleasure, guilty feelings, punishment feelings, self-dislike, self-criticalness, suicidal thoughts or wishes, crying, agitation, loss of interest, indecisiveness, worthlessness, loss of energy, changes in sleeping pattern, irritability, changes in appetite, concentration difficulty, tiredness or fatigue, and loss of interest in sex. Items are scored from 0 to 3, and higher scores indicate greater levels of severity. The ranges for depression are: 0-13 minimal, 14-19 mild, 20-28 moderate, and 29-63 severe. The BDI-II has high validity and reliability.

Beck Anxiety Inventory (BAI)⁹⁰. The BAI is a 21-item self-report scale that assesses the severity of anxiety symptoms. Items are scored from 0 to 3 (0 = not at all, 3 = severe). Higher scores indicate greater levels of severity, and the ranges for anxiety levels are: 0-9 normal to minimal, 10-18 mild to moderate, 19-29 moderate to severe, and 30-63 severe. The BAI consists of two factors: somatic and cognitive.

World Health Organization Quality of Life Assessment (WHOQOL)¹²². The WHOQOL-BRIEF is a 26-item brief version of the WHOQOL, that measures quality of life based on six domains: physical health, psychological state, level of independence, social relations, environment, and spirituality/religion/personal beliefs. Four general items about subjective overall QOL and health are also included. Only domain and general item scores are calculated in the WHOQOL-BREF. Items are scored on scales of 1 to 5, and higher scores indicate higher quality of life.

Patient Health Questionnaire (PHQ-9)¹²³. PHQ-9 is a self-administered instrument for screening, diagnosing, monitoring, and measuring the severity of depression. It rates the frequency of symptoms as "0" (not at all) to "3" (nearly every day) and has been validated for use in primary care. The PHQ-9 total score ranges from 0 to 27 and is categorized as follows: None or minimal depression 0-4, Mild depression 5-9, Moderate depression 10-14, Moderately severe depression 15-19, and Severe depression 20-27. Cronbach's alpha coefficients range from 0.86 to 0.89 and test-retest correlations range from 0.84-0.95 within 48 hours and from 0.81-0.96 at 7-day reassessment. PHQ-9 scores were found to be highly correlated with Beck Depression Inventory scores in the general population (r=0.73).

Generalized Anxiety Disorder Scale (GAD-7)¹²⁴. GAD-7 is a valid and reliable 7-question scale to screen for 4 anxiety disorders: Post Traumatic Stress Disorder, Panic Disorder, Generalized Anxiety Disorder, and Social Phobia. A score of ≥ 10 indicates a high probability of 1 or more of these disorders. Cronbach's alpha is 0.92 and test-retest correlation is 0.83. GAD-7 scores also correlate highly with scores of 2 commonly- used anxiety scales: the Beck Anxiety Inventory (r=0.72) and the anxiety subscale of the Symptom Checklist-90 (r=0.74).

Emotion Regulation Questionnaire (ERQ)¹²⁵. ERQ is a 10-item self-report survey assessing individual differences in the habitual use of two emotional regulation strategies: cognitive reappraisal (6 items)

and expressive suppression (4 items). Cognitive reappraisal is a strategy that involves interpreting an emotion-eliciting situation in a way that changes its emotional impact, whereas expressive suppression is a form of response modulation that involves restraining emotion expressive behavior. The ERQ shows high levels of internal consistency in measuring both strategies in a large, diverse sample (Reappraisal factor α =.79 and Suppression α =.73). Test-retest reliability across 3 months was .69 for both scales.

Penn State Worry Questionnaire (PSWQ)¹²⁶. The PSWQ is a 16-item questionnaire that aims to measure the trait of worry, using Likert rating from 1 (not at all typical of me) to 5 (very typical of me). Research suggests that the instrument has a strong ability to differentiate patients with generalized anxiety disorder (GAD) for other anxiety disorders.

Stanford Sleepiness Scale (SSS). The SSS is a single item subjective measure of sleepiness using a Likert rating from 1 (feeling active and vital) to 7 (almost in reverie).

Consensus Sleep Log¹²⁸. The consensus sleep log contains information from seven days of reporting the following measures: Wake after Sleep onset (WASO), Time in Bed (TIB), Sleep onset Latency (SOL), Total Sleep Time (TST), caffeine and alcohol use, and naps.

Profile of Mood States(POMS)¹²⁸. The POMS is a questionnaire with 24 items and four scales to assess mood. The four scales are depression and anxiety, fatigue, vigor, and irritability. These scales are internally consistent and have good scale fit.

Snaith-Hamilton Pleasure Scale (SHAPS). The Snaith-Hamilton Pleasure Scale (SHAPS) is a self-administered, paper-and-pencil questionnaire with 14 items assessing four domains of pleasure response/hedonic experience: interest/pastimes, social interaction, sensory experience, and food/drink.

CHICa (Irritability and Cognitive Subscales)¹²⁹. The CHICa is a 26 item self-report measure of impaired thermoregulation, disrupted appetite, affective problems, and lowered level of cognitive functioning. Each question is a four-point scale from 0 ('definitely no/untrue') to 3 ('definitely yes/true').

Difficulty in Emotion Regulation Scale (DERS). The DERS is a 36 item self-report measure of emotion regulation deficits that is designed to capture clinically relevant problems.

SF-36 (RAND) Version 1¹³⁰. The SF-36 is a 36-item, self-administered survey to assess comprehensive quality-of-life measures. It consists of eight sections: vitality, physical functioning, bodily pain, general health perceptions, physical role functioning, emotional role functioning, and mental health. This survey is widely used and has been proven to be a reliable indicator of quality-of-life measures.

Toronto Alexithymia Scale (TAS-20)¹³¹. The TAS-20 is a 20-item self-report measure of alexithymia from multiple perspectives: difficulty identifying and distinguishing between feelings and bodily sensations, difficulty describing feelings, reduced daydreaming, and externally-oriented thinking.

Ruminative Response Scale (RRS-Short). The RRS is a 10-item questionnaire that measure ruminative tendencies.

Ford Insomnia Response to Stress Test (FIRST)¹³². The FIRST is a 9 item questionnaire regarding sleep disturbance in response to commonly experienced stressful situations, such as before an important meeting the next day or after an argument.

Credibility/Expectancy Questionnaire¹³³. The Credibility/Expectancy Questionnaire is a scale for measuring treatment expectancy and rationale credibility. The questionnaire derives two predicted factors: cognitive based credibility and relatively more affectively based expectancy. The participant will see one section related to thinking and one section related to feeling. It has high internal consistency within each factor and good test-retest reliability.

Working Alliance Inventory¹³⁵. The Working Alliance Inventory is a measure of therapeutic alliance assessing three aspects: agreement on the tasks of therapy, agreement on the goals of therapy, and

development of an affective bond. A high score on the survey is associated with improved outcomes for clients. The reliability compared to the Helping Alliance Questionnaire was good (α > 0.80).

Treatment Adherence Survey. The Treatment Adherence Survey is a self-report survey assessing the participant's adherence to the insomnia treatment.

Treatment Satisfaction Survey. The Treatment Satisfaction Survey is a self-report survey assessing the satisfaction and effect of the insomnia treatment.

